Study Sites (with site lead contact information):	
St. Boniface General Hospital [name]/[name] CR3012-I.H. Asper Institute [name] [contact] [contact] Email: [contact]
 
Saint John Regional Hospital - New Brunswick Heart Centre [name] [name] [contact] Email: [contact]
 
Queen Elizabeth II Health Sciences Centre [name] [name] [contact] [contact] Email: [contact]
 
Montreal Heart Institute [name] [name] [contact] Email: [contact]
 
Quebec Heart and Lung Institute (University of Laval) [name] [name] [contact]) Email: [contact]
	
Study Design:	A five centre prospective, randomized, open, blinded endpoint (PROBE) controlled trial using assessor blinding and intention-to-treat analysis.	
Expected number of participants:	244 individuals (122 in each arm) split up evenly between five study sites.	
Intervention:	Patients in the Prehab group will receive, in addition to the standard of care, a	

“The PREHAB Study” (Pre-operative Rehabilitation for reduction of Hospitalization After coronary Bypass and valvular surgery.)

	
four to eight-week comprehensive exercise therapy and education program at a community-based CR facility (see details in appendix). Patients will be asked to complete at least two sessions of supervised, structured exercise class plus have the option to attend one additional exercise class per week for a minimum of four weeks up to the time of their surgery, with progression to a moderate to high-intensity interval program based on the supervised assessment of the patient’s capabilities.
 
Prehab participants will also attend four education sessions on topics such as risk factor reduction, medication use, cardiovascular physiology, smoking cessation, healthy eating, exercise, and stress management and promotion of self-managed care.

Duration per participant:	~ 4-8 weeks
Inclusion criteria (all need to be fulfilled for eligibility):	
 1. Patients, aged 60 years or older, undergoing elective isolated coronary artery bypass grafting (CABG), aortic valve repair/replacement for moderate aortic stenosis or severe regurgitation, mitral valve repair/replacement for moderate stenosis or severe regurgitation or combined CABG/valve procedures. 2. Patients with Clinical Frailty Score (CFS) ≥ 3 (managing well) and < 7 (8 = very severely frail, approaching end-of-life or 9 = terminally ill) at time of acceptance for cardiac surgery. 3. Patients with an estimated ≥ 4 week wait time.
Exclusion criteria (any of the following factors will result in ineligibility):	
 1. Patients who have unstable or recent unstable cardiac syndrome as defined by: 
 • Severe heart failure (NYHA IV) or angina (CCS class IV) symptoms. • Critical left main (LM) coronary disease. Hospitalization for arrhythmias • CHF or acute coronary syndrome prior to randomization. 2. Patients who have severe left ventricular obstructive disease (defined by): 
 • Severe aortic or mitral stenosis (aortic or mitral valve area $<1.0\text{cm}^2$ or mean gradient $> 40 \text{ mmHg}$ or $> 10\text{mmHg}$ respectively) • Dynamic left ventricular (LV) outflow obstruction. 3. Patients who have demonstrated exercise induced ventricular arrhythmias or have experienced a recent hospitalization for arrhythmias; 4. Patients who have cognitive deficits that would preclude rehabilitation; 5. Patients who have physical limitations that would preclude rehabilitation; 6. Patients who are unable to attend the Prehab program.
Primary outcomes:	Proportion of patients with hospital length of stay >7 days
Secondary outcomes:	(1) pre-operative frailty, (2) exercise capacity, (3) physical activity behavior, (4) in-hospital outcomes, (5) 1-year clinical outcomes, (6) 1-year health-related quality of life, (7) cost-analysis.
Safety:	Safety data including new hospitalization, worsening angina or heart failure and arrhythmias will be captured and all adverse events will be reportable to the

“The PREHAB Study” (Pre-operative Rehabilitation for reduction of Hospitalization After coronary Bypass and valvular surgery.)

	
study Data Safety Monitoring Board (DSMB).
 
Safety Monitoring: Clinical stability during the pre-habilitation period is to be evaluated twice per week by the CR team using clinical questioning in comparison to their baseline stress test. All cases will be reviewed in conjunction with the attending physician.

Statistical methods and sample size calculation:	
The sample size calculation was based on the primary objective – determining the effect of Prehab on rates of prolonged hospital length of stay > 7 days. Our preliminary data, demonstrated the proportion of frail patients in the Control group with a hospital length of stay > 7 days to be 58.3%. For the Prehab group, based on improvements in functional capacity in our pilot RCT and the work by Arthur et al.¹⁴, we believe an absolute 20% reduction in proportion of patients that require prolonged hospital length of stay of greater than 7 days, is feasible. A sample size of 194 individuals (97 in each group) will be required for a two-tailed test at an alpha of 0.05 and power of 80%. All patients assigned to the pilot Prehab group completed the intervention, however, we are mindful that we will be recruiting frail, elderly patients who may have a higher dropout rate. Hence, we are estimating a 20% dropout rate and plan to recruit 244 individuals (122 in each study arm) to achieve an eventual sample size of 194 after dropout.

Time schedule:	
Planned start of study: April 2014
 
Planned end of study: May 2017
 
Planned duration: 3.5 years

Table of Contents

Study Synopsis	1
Table of Contents	4
Terms and Abbreviations	8
Executive Summary.....	10
1 General Information	11
1.1 Title.....	11
1.2 Study Management Committee.....	11
1.3 Coordinating Centre	11
2 Background and Rationale for Project	11
2.1 Introduction	11
2.2 Exercise Rehabilitation.....	11
2.3 Identification of Potential Opportunity	12
2.4 The PREHAB Study – Primary Research Questions/Hypotheses	12
3 Study Design.....	12
3.1 Methodological Approach	12
3.1.1 Preliminary Data Informing Study Methodology.....	12

“The PREHAB Study” (Pre-operative Rehabilitation for reduction of Hospitalization After coronary Bypass and valvular surgery.)

3.2 Study Design, Setting, Population.....	14
3.3 Eligibility Criteria	14
3.3.1 Inclusion Criteria (all need to be fulfilled for eligibility).....	14

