2.4 The PREHAB Study – Primary Research Questions/Hypotheses

The primary research question(s) for the *Prehab* study include:

- i. What is the effect of a preoperative cardiac pre-habilitation (“*Prehab*”) program on the proportion of patients with hospital length of stay (*LOS*) > 7 days.
We hypothesize that the performance of a multifaceted, interdisciplinary cardiac “*Prehab*” program in patients awaiting an elective cardiac surgery will reduce the proportion of frail elderly patients requiring a postoperative hospital *LOS* > 7 days.
- ii. What is the effect of a preoperative cardiac pre-habilitation program in high-risk frail elderly patients on (1) pre-operative frailty, (2) exercise capacity, (3) self-managed physical activity behavior, (4) in-hospital outcomes, (5) 3-month clinical outcomes, and (6) 3 month health-related quality of life.
We hypothesize that the “*Prehab*” program for frail elderly patients awaiting an elective cardiac surgery will reduce frailty, improve exercise capacity, improve self-managed physical activity behavior, improve in-hospital outcomes, improve clinical outcomes 3 months and 1 year postoperatively, and improve health-related quality of life.

3 Study Design

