5.1.1 Primary Outcome

Proportion of patients with hospital length of stay >7 days.

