5.2 Statistical/Analytical Plan

Objective 1: To determine if *Prehab* reduces the proportion of frail elderly patients requiring a prolonged hospital length of stay of >7 days. A univariable analysis will be undertaken to determine if hospital *LOS* > 7 days is associated with frailty and other patient-level factors. A stepwise multivariable logistic regression model will then be developed to determine if *Prehab* attendance is independently associated with a decreased risk of prolonged hospital length of stay > 7 days. As a secondary analysis, hospital *LOS* will also be compared as a continuous variable between the *Prehab* and standard care groups using a Mann-Whitney test.

“The PREHAB Study” (Pre-operative Rehabilitation for reduction of Hospitalization After coronary Bypass and valvular surgery.)

Objective 2: Does attending *Prehab* influence frailty, exercise capacity, physical activity behavior, in-hospital complications, and *HRQoL*? Although we will employ four different measures of frailty, based on our preliminary data and based on a Task Force’s position statement(90), the Modified Fried Criteria will be the primary frailty outcome over time from baseline to the end of *Prehab* program (pre-operatively), or from baseline to the 3-month post-operative follow-up. The primary measure of exercise capacity will be the *6MWT* and will be analysed with univariable linear regression models to evaluate the association between the *6MWT* and *Prehab* attendance. Accelerometers will be used to objectively measure the number of minutes spent performing moderate to vigorous physical activity (*MVPA*) and total physical activity (*TPA*) per day for a period of 7 days and compared between groups. A composite outcome for a major adverse cardiac event (i.e. *MACCE* = in-hospital stroke, myocardial infarction, renal failure requiring dialysis and death) and delirium will be compared between groups using a Chi-Square or Fisher’s Exact test. A multivariable logistic regression will be used to identify if *Prehab* is independently associated with in-hospital delirium. The *SF-12v2* and *EQ-5D* scores, after normative standardization, will be analyzed through use of a repeated *ANOVA* to allow for a standardized group and group/time interaction effect estimation.

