5.3 Sample Size Calculation

The sample size calculation was based on the primary objective – determining the effect of *Prehab* on rates of prolonged hospital length of stay > 7 days. Our preliminary data, demonstrated the proportion of frail patients in the Control group with a hospital length of stay > 7 days to be 58.3%. For the *Prehab* group, based on improvements in functional capacity in our pilot *RCT* and the work by Arthur et al14, we believe an absolute 20% reduction in proportion of patients that require prolonged hospital length of stay of greater than 7 days, is feasible. A sample size of 194 individuals (97 in each group) will be required for a two-tailed test at an alpha of 0.05 and power of 80%. All patients assigned to the pilot *Prehab* group completed the intervention, however, we are mindful that we will be recruiting frail, elderly patients who may have a higher dropout rate. Hence, we are estimating a 20% dropout rate and plan to recruit 244 individuals (122 in each study arm) to achieve an eventual sample size of 194 after dropout.

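### The trial is sized on a 20-point fall in the proportion staying more than 7 days, but section 5.2 plans no between-arm estimate or confidence interval on that scale

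*Combined protocol and SAP*

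**What the plan says.** Section 5.1.1 defines the primary outcome as "Proportion of patients with hospital length of stay >7 days". Section 2.4 asks about the effect of the programme "on the proportion of patients with hospital length of stay" above 7 days, and hypothesises that it "will reduce the proportion of frail elderly patients requiring a postoperative hospital" stay of that length. Neither place names an absolute or a relative scale.

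The scale appears in the sample-size text, which is the same in the synopsis and section 5.3. The control rate comes from preliminary data that put "the proportion of frail patients in the Control group with a hospital length of stay > 7 days to be 58.3" per cent. The target is stated as "we believe an absolute 20% reduction in proportion of patients that require prolonged hospital length of stay of greater than 7 days". The calculation uses a "two-tailed test at an alpha of 0.05 and power of 80" per cent, giving 97 evaluable patients per arm and 122 recruited per arm after 20% dropout.

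Under Objective 1, section 5.2 plans three analyses:

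- a univariable analysis of the association between long stay and frailty or other patient-level factors;
- a stepwise multivariable logistic model, whose stated purpose is to show whether attending the programme is "independently associated with a decreased risk of prolonged hospital length of stay > 7 days";
- a Mann-Whitney test of length of stay as a continuous variable, as a secondary analysis.

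**The concern.** None of the three analyses is described as producing the quantity the trial was sized to detect. The univariable step is described in terms of patient factors, not arms. The Mann-Whitney test gives no difference in proportions. The logistic model compares the groups, but on the odds scale and conditional on whichever covariates are kept. No risk difference, risk ratio or confidence interval is specified, and no direct comparison of the two proportions is planned. By contrast, the same section plans a chi-square or Fisher's exact comparison of groups for the major adverse event composite and for delirium.

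Two things are at stake. First, there would be no prespecified estimate, with its uncertainty, to set against the 20-point target. Second, a long stay is expected in roughly half the patients. At that frequency an odds ratio lies much further from 1 than the risk ratio, so it is easily misread when the accompanying text speaks of risk.

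**Working it through.** **Inputs.** Control risk p_C = 0.583 (5.3). Target risk p_P = 0.583 - 0.200 = 0.383 (synopsis, 5.3). Two-sided alpha 0.05, power 80%, 97 evaluable per arm and 20% dropout (5.3).

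**1. Reproduce the sample size.** Two-proportion test with pooled variance and no continuity correction; mean risk 0.483:

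n = [1.96·√(2·0.483·0.517) + 0.842·√(0.583·0.417 + 0.383·0.617)]² / 0.200²

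= (1.385 + 0.583)² / 0.04 ≈ 96.8, so 97 per arm and 194 in total.

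Dropout: 97/0.8 = 121.25, so 122 per arm and 244 in total. Both stated figures are reproduced. A 20% *relative* reduction (0.583 × 0.8 = 0.466) would need 287 per arm, so the plan was clearly sized on the absolute difference.

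**2. The same design effect on three scales.**

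| Measure | Calculation | Result |
|---|---|---|
| Risk difference | 0.383 - 0.583 | -20.0 points |
| Risk ratio | 0.383/0.583 | 0.657 (34% lower risk) |
| Odds ratio, unadjusted | (0.383/0.617)/(0.583/0.417) | 0.444 (56% lower odds) |

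Standard error of the difference at 97 per arm: √[(0.583·0.417 + 0.383·0.617)/97] = 0.0703. The Wald 95% CI is -0.200 ± 1.96·0.0703, or -33.8 to -6.2 points.

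**3. If the odds ratio were read as a risk ratio.** The implied *Prehab* risk would be 0.444 × 0.583 = 25.9%, a fall of 32.4 points instead of 20.0.

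**4. A smaller effect.** For a result that is just significant at 97 per arm (58.3% vs 44.0%, pooled z = 1.99), the difference is -14.3 points, the risk ratio 0.75 and the odds ratio 0.56.

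**5. Dependence on covariates.** A conditional odds ratio moves away from 1 as prognostic covariates enter, even with perfect randomisation. To illustrate this, I assume that the adjusted covariates form a normal prognostic score with standard deviation s on the logit scale. For each arm, solve for a in E[1/(1 + exp(-(a + sZ)))] = marginal risk, with Z standard normal. The conditional odds ratio is then exp(a_P - a_C). The marginal risks stay at 58.3% and 38.3% throughout.

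| s (assumed) | Conditional odds ratio |
|---|---|
| 0 | 0.444 |
| 0.5 | 0.423 |
| 1.0 | 0.375 |
| 1.5 | 0.318 |

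The documents do not say how prognostic the retained covariates would be, so this is a range and not a prediction.

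**6. One odds ratio does not fix the absolute effect.** An odds ratio of 0.444 corresponds to a fall of 20.0 points at a control risk of 58.3%. At 37.7% (the non-frail rate in Table 6) it corresponds to 16.5 points, and at 80% (assumed) to 16.0 points.

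**The case against.** A reader might infer that the plan has chosen an odds ratio as its effect estimate, that this fails to answer the trial's question, and that it will overstate the benefit. The documents do not support this stronger reading, for four reasons.

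- The term odds ratio does not appear in section 5.2. The section names no effect estimate at all; the odds ratio is only what a logistic model yields by default.
- The reference to decreased risk is a yes/no statement about direction, and an odds ratio below 1 does mean lower risk. An odds ratio of 0.44 is correct on its own scale. It exaggerates only if someone reads it as a risk ratio, and no passage does so.
- Sections 2.4 and 5.1.1 refer to a proportion without naming a scale. Sizing on a difference in proportions does not oblige a trial to use the risk difference as its estimate. A logistic model with prespecified covariates can validly test for no effect, and a risk difference can be derived from it.
- Reporting the outcome by arm would give the crude difference. The preliminary Table 6 reports counts and percentages for this endpoint beside a column correctly labelled OR.

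All of this stands, and it limits the claim. The gap itself remains: no between-arm estimate with a confidence interval is prespecified on the scale of the design. Table 6 also shows how the misreading could arise. Its title speaks of risk and its only effect column is the odds ratio. For this endpoint (42/72 vs 23/61) the odds ratio is 2.31, while the risk ratio is 1.55 and the difference 20.6 points.

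**Conclusion.** The point holds as a specification gap that should be closed. The primary question concerns a proportion and the sample size an absolute 20-point fall, but section 5.2 specifies no between-arm estimate or interval on that scale. The gap between 34% lower risk and 56% lower odds follows from the plan's own design rates. It becomes an overstatement only if the odds ratio is read as a risk ratio. The conditional range of about 0.42 to 0.32 rests on the assumed covariate strength (s from 0.5 to 1.5); with weak covariates it stays close to the unadjusted 0.44. The sample size is not in question. Stepwise selection, and the use of attendance as the exposure despite the intention-to-treat statement in section 3.2, are separate problems. The missing effect measure would remain after both were corrected.

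**What to change.** In section 5.2, under Objective 1, state the following:

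- The primary effect measure is the difference between randomised arms, by intention to treat, in the proportion with a hospital stay above 7 days, with a 95% confidence interval.
- It is estimated in one of two ways, chosen in advance. One is the unadjusted difference. The other is standardisation from a logistic model containing randomised arm and prespecified baseline covariates: average the predicted probabilities over all analysed patients under each arm, then subtract, with delta-method or bootstrap standard errors.
- There is no stepwise selection in this model. Delta-method errors computed on a selected model would ignore the selection step.
- The risk ratio comes from the same step. Any odds ratio is labelled as an odds ratio and is supplementary.
- The estimate and its interval are interpreted against the 20-point target.

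The cost is a change of wording and a few lines of code. Recruitment stays at 122 per arm. The drawback for the sponsor is a relative effect that looks less favourable than the odds ratio would.

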Figure 2 - (Panel A) Flowchart of preliminary frailty study cohort recruitment over a 12-month period (July 9, 2012-July 31, 2013). Overall consent rate 77% with a study completion rate of 73%.....	42
Figure 3 - (Panel A): Total walking distance achieved by Standard care and Prehab patients during a 6-minute walking test. Values are mean \pm standard error; Standard care n= 7; Prehab n=7. a different from baseline ($p<0.05$); # different from Standard care ($p<0.05$). Preop= one week pre-operatively; Postop= three months post-operatively.....	43
Figure 4 - Proposed PREHAB Study Process Overview – Recruitment and Study Protocol	44
Figure 5 - A. Predicted Flow of Patients Per 14 Month Planned enrollment period. B: Projected Study Timeline. C: Timeline for Individual Objectives	45
Appendices.....	46
Appendix I - Modified Fried Criteria (1-7).....	46
Appendix II - Five item Geriatric Depression Scale (5-GDS).....	47

“The PREHAB Study” (Pre-operative Rehabilitation for reduction of Hospitalization After coronary Bypass and valvular surgery.)

Appendix III - The Patient Health Questionnaire (PHQ-9)	48
Appendix IV – Pilot Project Manuscript	Error! Bookmark not defined.
References	56

Terms and Abbreviations

5-GDS	5-point geriatric depression scale. See Appendix II - Five item Geriatric Depression Scale (5-GDS)
6MWT	6 Minute Walking Test. See 3.5.5.4.2 Exercise stress test and 6-minute walk test (6MWT) .
ACSM	American College of Sports Medicine. http://www.acsm.org
ADL	Activities of Daily Living. From Older Americans Resources and Services Scale. See http://centerforaging.duke.edu/services/141 .
ANOVA	Analysis of Variance
CABG	Coronary Artery Bypass Graft
CAM-ICU	Confusion Assessment Method for the Intensive Care Unit. See http://www.icudelirium.org/docs/CAM_ICU_training.pdf
CCS	Canadian Cardiovascular Society.
CES-D Scale	The two-item Center for Epidemiologic Studies Depression (CES-D) Scale. See http://www.scireproject.com/outcome-measures-new/center-epidemiological-studies-depression-scale-ces-d-and-ces-d-10
CFS	Clinical Frailty Score
Charlson Co-morbidity Index	See http://www.ncbi.nlm.nih.gov/pubmed/3558716?dopt=Abstract
CHF	Congestive Heart Failure
COPD	Chronic Obstructive Pulmonary Disease.
CR	Cardiac Rehabilitation program. See 3.5.5.3 Core Components of Cardiac Rehabilitation .
CRF	Case Report Form
CVD	Cerebrovascular Disease
DSMB	Data Safety Monitoring Board
EQ-5D	EuroQual-5D (EQ-5D). See http://www.euroqol.org/ .
EuroSCORE II	See http://www.euroscore.org/calc.html .
FI	Frailty index.
Functional Co-morbidity Index	See http://www.ncbi.nlm.nih.gov/pubmed/15878473 .
GXT	Graded maximal exercise stress test. See 3.5.5.4.2 Exercise stress test and 6-minute walk test (6MWT)
HQP	Highly Qualified Personnel
HREB	Human Research Ethics Board
HRQoL	Health Related Quality of Life
IADL	Instrumental Activities of Daily Living
ICU	Intensive Care Unit.
iKT	Integrated Knowledge Translation
IQR	Interquartile Range
LM	Left Main coronary artery
LOS	Length of Stay.
LV	Left Ventrical
MACCE	Major Adverse Cardiac and Cerebral Event
MI	Myocardial Infarction
MoCA	Montreal Cognitive Assessment. See http://www.mocatest.org/ .
Modified	See Appendix I - Modified Fried Criteria (1-7)

“The PREHAB Study” (Pre-operative Rehabilitation for reduction of Hospitalization After coronary Bypass and valvular surgery.)

MVPA	Moderate to Vigorous Physical Activity
NYHA	New York Heart Association. http://www.heart.org/HEARTORG/Conditions/HeartFailure/AboutHeartFailure/Classes-of-Heart-Failure_UCM_306328_Article.jsp
OARS scale	Older Americans Resources and Services Scale. See http://centerforaging.duke.edu/services/141 .
PREHAB	Title of study. “Pre-operative Rehabilitation for reduction of Hospitalization After coronary Bypass and valvular surgery.”
Prehab	Refers to the preoperative cardiac pre-habilitation study intervention. For complete definition see section 3.5.5 Prehab Intervention .
PROBE	Rrospective, Randomized, Open, Blinded Endpoint trial.
PVD	Peripheral Vascular Disease.
RASS	Richmond Agitation and Sedation Scale. See http://www.icudelirium.org/docs/RASS.pdf
RCT	Randomized Controlled Trial
REDCap	See http://project-redcap.org/ .
ROC analysis	Receiver Operating Curve analysis.
SF-12v2	The Short Form-12 (SF-12v2)
SPPB	Short Physical Performance Battery. See http://www.ndorms.ox.ac.uk/prove/documents/assessors/outcomeMeasures/SPPB_Protocol.pdf
StandC	Standard Care (control group)
STS-PROMM	See http://riskcalc.sts.org/ .
TECH VALUE NET	Technology Evaluation in the Elderly Network
TPA	Total Physical Acitity

Executive Summary

Background: More than half of all cardiac surgeries in Canada are performed on patients aged 65 years and older. Although cardiac surgery is generally safe, there is evidence indicating that elderly patients who are frail prior to surgery have a longer hospital length of stay in addition to higher rates of major complications and mental health disorders after surgery, as compared to non-frail, elderly patients. Therefore, it is critically important for the health care team to identify strategies that will provide improved patient outcomes through appropriate, safe and effective care for frail elderly patients, and furthermore will engage and empower patients in ongoing self-managed care. In Canada, when a patient requires heart surgery, they are placed on a “waiting list”. Patients can wait for elective heart surgery for as long as 3-4 months. Fortunately, this waiting system is “safe” and very few patients die while waiting for heart surgery. However, many patients on the waiting list experience feelings of powerlessness and are fearful of “making things worse”, which cause them to stop being active and to become even more weakened prior to their operation. A solution to address this problem is to “de-frail” the high-risk patient to ensure that they are better prepared to survive and thrive after cardiac surgery.

Objective: We anticipate that the proposed project will inform clinical practice and facilitate the development of a treatment that will ensure that older patients both survive and thrive after their heart operation.

Methods: We will conduct a clinical trial where frail patients waiting for heart surgery are randomly chosen to either receive the current standard of care or to participate in a 4-8week exercise/education “Pre-habilitation” program at a community-based cardiac rehabilitation facility in one of five cities (Winnipeg, MB; Saint John, NB; Halifax, NS; Montreal, QC; Saint-Foy, QC). Patients who refuse to be randomized or are deemed “unsafe” to participate in the exercise portion of the study but still wish to participate will be enrolled in a follow up registry. We will also plan to work with local health authorities and national advocacy bodies to ensure that this program is sustainable in the real-world in the future.

Significance/Impact: The geriatric population is one of the fastest growing demographics undergoing cardiac surgery in North America (1)(2). With this, the geriatric syndrome, defined as a “constellation of symptoms and signs [that] describe the heterogeneous response of older adults to physiological and metabolic challenges,”(3) has become an important consideration in patients undergoing cardiac surgery. To date, no high-quality study has prospectively examined the impact of preoperative cardiac rehabilitation in the frail-elderly undergoing cardiac surgery and represents a noticeable knowledge gap. The *Prehab* study is specifically aimed to improve the care and establish best practice in frail elderly patients undergoing high-risk cardiac surgery procedures through a rigorous evaluation of the utilization of an inter-disciplinary and multimodal patient optimization protocol. Importantly, we have also planned for a detailed study analysis by key stakeholders at the health region level to determine optimal methodologies to implement this program following the completion of this investigation. Reducing anxiety, improving exercise capacity, promoting a healthy lifestyle that is durable (i.e. long-lasting) and improving *HRQoL* in the elderly are the over-riding goals of this endeavour.

1 General Information

